2.1 Primary endpoint

The primary outcome measure was the proportion of patients without sore throat after 3 days of therapy, as evaluated by the Investigator according to the Tonsillopharyngitis Severity Score (TSS), in both Angal S and ANTI-ANGIN® FORMULA arms.

TSS, a questionnaire (point scale) for healthcare professionals, is used in clinical practice as well as clinical trials to evaluate dynamic changes of symptoms severity of the infection-inflammatory process in the throat (Bereznoy VV, Riley DS, Wassmer G, Heger M. Efficacy of extract of Pelargonium sidoides in children with acute non-group A beta-hemolytic streptococcus tonsillopharyngitis: a randomized, double-blind, placebo-controlled trial). One of such clinical trials with TSS questionnaire was conducted in 2005 in Germany, ©CRO Applertee AG. A version of TSS ©CRO Applertee AG was adapted for this protocol.

TSS (Tonsillopharyngitis Severity Score) is a questionnaire for evaluation of the following symptoms severity: pharyngalgia, difficulty in swallowing, salivation, hyperemia of pharyngeal mucosa, and body temperature increase according to a 4-point scale:

```
0 = \text{no symptom};
```

- 1 = insignificant symptom;
- 2 = moderate symptom;
- 3 = significant symptom.

The axillary body temperature increase is rated as follows:

```
0 points: <37.5 °C;
```

- 1 point: 37.5 to <38.5 °C;
- 2 points: 38.5 to <39.5 °C;
- 3 points: ≥39.5 °C.

TSS is filled in by the Investigator based on the patient complaints and physical examination data. The Investigator summarizes the points obtained for every symptom to obtain a total sum of TSS points. A total sum of TSS points will be evaluated at screening to define the inclusion criteria and evaluate for the baseline level; measure efficacy of the therapy conducted in the both arms at Visit 2 (Day 4); as well as evaluate the disease outcome at Visit 2 (Day 4) and/or Visit 3 (Day 5), if applicable.

2.2 Secondary endpoints

- The frequency of ≥50% total score reduction according to the TSS questionnaire completed by the Investigator as compared to the baseline in both Angal S and ANTI-ANGIN® FORMULA groups at Visit 2 (Day 4).
- Total score reduction according to the TSS questionnaire, as well as a reduction in the symptoms (sore throat, difficulty in swallowing, salivation, erythema, and fever) after a 3-day therapy, at Visit 2 (Day 4), as compared to the baseline total score.
- A period of time required for disappearance of the disease symptoms, determined according to the patient's diary (subjective patient's evaluation), but no more than 5 days during the trial—for patients who have achieved the corresponding outcome.
- A proportion (%) of patients who fully recovered by Day 4 in Group A and by Day 5 in Group B (the outcome of a disease according to the objective evaluation by the Investigator, the total score according to the TSS questionnaire ≤ 2).
- A change in the sore throat intensity by 100 mm VAS (visual analogue scale filled in by the patient) at the beginning, after 3 days of therapy, and at the end of treatment in both groups.

VAS (visual analogue scale) to evaluate pharyngalgia severity:

The patient will fill in this scale at every visit to the trial site (Visits 1, 2, 3, where applicable). Calibrated scales 100 mm in length with the relevant measuring instruments will be provided for the clinical trial.

The patients should evaluate their pain severity according to VAS at every visit (if possible, before administration of the painkillers (if those are required) or the study drug/comparator drug).

2.3 Evaluation of the study drug safety and tolerance

Safety of the trial therapy is evaluated based on the systemic parameters (systolic and diastolic blood pressure, breathing rate, heart rate, body temperature, ECG), laboratory tests results, frequency of adverse events (AEs) and serious adverse events (SAEs). AEs nature and incidence (allergic reactions, burning sensation, discomfort) at the administration site will be evaluated throughout the trial. Global evaluation of treatment tolerability will be made by the patient and the physician according to the following scale:

Scores	Evaluation
0	Poor

1	Satisfactory
2	Good
3	Excellent

Evaluation of the study drug tolerability by the patient and the physician (points/scores) should be specified in the eCRF at Visits 2 or 3 (where applicable).

3 Main provisions for analysis

3.1 Study drugs and therapy schedule

The patients were randomized in 1:1 ratio to the following groups:

Main group: Angal S, topical spray [menthol], 0.5 mg + 2 mg/1 ml (Sandoz d.d., Slovenia), 3 to 5 consecutive presses on the actuator button, 6 to 10 times per day, for 4 days or until full recovery (whichever occurs first during 4 days of therapy).

Control group: ANTI-ANGIN[®] FORMULA, topical metered spray, 1–2 sprays at a time, up to 6 times a day, for 5 days or until full recovery (TSS \leq 2) (whichever occurs first during 5 days of therapy).

3.2 Serious protocol deviations

A serious protocol deviation (Item 11.3 of the trial protocol) is a deviation, which may, according to the estimate by the Investigator or a person assigned by the Investigator, result into withdrawal of the subject from the trial or withdrawal of his data from the statistical part of the trial. The deviations not referred to as serious ones shall be considered minor protocol deviations.

For the purposes of this analysis, the serious protocol deviations were defined as follows:

Description	Example/Explanation	Efficacy or safety	Excluded from population:
lincilision and non-	Inclusion criterion No. 5: e.g., inclusion of the patient with initial total TSS < 5	Efficiency	PP
Violation of the informed consent receipt procedure	Absence of the Informed Consent Form	Safety and efficacy	All

	Informed Consent Form was signed after randomization/initiation of therapy	Safety and efficacy	None
	Prescription of the drug non-consistent with the randomization arm	Efficiency	PP
	Low compliance: the patient missed more than 3 doses of the study drug	Efficiency	PP
Concomitant drugs	The patient used prohibited drugs during the trial (or had used the drugs prohibited by the inclusion/exclusion criteria before the trial initiation)	Efficacy and safety	PP

A final list of serious protocol deviations will be compiled before the statistical analysis start. Every protocol deviation should be evaluated for the patient's exclusion from the PP data set or statistical analysis by the trial Sponsor representative. The decisions adopted and lists of patients included into the relevant data sets must be documented before the analysis initiation.

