- Demographic data (date of birth, sex, age);
- Measurement of weight and height;
- Anamnesis gathering;

- Records on the concomitant therapy;
- Evaluation of inclusion/non-inclusion criteria;
- Evaluation of the throat pain intensity according to VAS;
- Fill-in of TSS questionnaire by the Investigator;
- Physical examination (including oropharynx);
- Measurement of the main vital signs;
- Hematology;
- Biochemistry;
- Urine pregnancy test;
- 12-lead ECG;
- Evaluation of inclusion/non-inclusion criteria;
- Randomization;
- Dispensing of the study drugs;
- Provision with the patient's diaries and training on the fill-in rules;
- Initiation of therapy with the study drugs;
- Evaluation of adverse events (including based on results of the throat and pharynx examination).

After the screening tests completion, on the same day, the patients who meet all the inclusion criteria will be randomized into one of the two trial groups (arms): Angal S or ANTI-ANGIN® FORMULA. Therapy group will be assigned by randomization (in 1:1 ratio). The patients will be given the relevant study drugs and the patient's diaries.

The patients will be instructed on how to fill in the patient's diary.

The patients will be instructed on how to use the spray (Angal S or ANTI-ANGIN® FORMULA) and position it correctly in the mouth cavity.

Only after the training the patients will be allowed to start the trial treatment. The first use of the drug (spray) corresponding to the assigned therapy group on Day 1 after randomization will be considered to be the treatment initiation (for both groups).

Group A, Angal S, topical spray; one dose includes 3 to 5 consecutive presses on the actuator button, six to ten times per day,

for up to 4 days or until full recovery (whichever occurs first during 4 days of therapy). While breath is held, the drug should be sprayed on oral and pharyngeal mucous membrane.

Group B, ANTI-ANGIN® FORMULA, topical metered spray; one dose includes 1 to 2 consecutive presses on the actuator button, up to 6 times per day, for 5 days or until full recovery (whichever occurs first during 5 days of therapy). While breath is held, the drug should be sprayed on oral and pharyngeal mucous membrane.

Visits during therapy with Angal S or ANTI-ANGIN® FORMULA

During Days 2 and 3 of the therapy, the patients (in both groups) do not visit the trial site.

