4.4.3 Labeling of the study drugs

As this is an open trial, the trial site will be provided with the packed products from the series commercially available in the EU (study drug) and Russia (comparator drug). Every carton box with the drugs will contain a self-adhesive label with the data listed below:

- "For clinical trials only";
- A protocol number;
- Title, address, and phone number of the trial site;
- Title, address, and phone number of the trial Sponsor;
- A field for a patient's randomization number.

The label should not overlap the drug name, active substances, and their strength, shelf life, manufacturer's name.

At the screening visit, every patient in the study drug group will be given 1 bottle (vial) of Angal S (150 doses), and every patient in the comparator drug group will be given 1 bottle (vial) of ANTI-ANGIN® FORMULA (100 doses). The dispensed

amounts are sufficient for the trial completion according to the protocol.

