4.4.4 Strength and dosage regimen of the study drugs

Angal S, topical spray [menthol], 0.5 mg + 2 mg/1 ml (Sandoz d.d., Slovenia), the study drug, will be used according to Prescribing Information in the following way: 3 to 5 consecutive presses on the actuator button, 6 to 10 times per day, for 4 days or until full recovery (TSS \leq 2), whichever occurs first during 4 days of therapy. One dose of Angal S is 3 to 5 consecutive presses.

ANTI-ANGIN® FORMULA, topical metered spray, 0.12 mg + 0.24 mg/dose (OOO Valeant, Russia), the comparator drug, will be used according to Prescribing Information in the following way: 1 to 2 consecutive presses on the actuator button, up to 6 times per day, for 5 days or until full recovery (TSS \leq 2), whichever occurs first during 5 days of therapy. One dose of ANTI-ANGIN® FORMULA is 1–2 sprays.

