6.3 Methods to monitor the subjects' compliance with trial procedures

At every visit after Visit 1, the subjects' compliance will be checked by counting the unused drug and analysis of the patient's diaries.

The protocol envisages the dose of Angal S, the study drug, as 3 to 5 consecutive presses on the actuator button, 6 to 10 times per day, and ANTI-ANGIN® FORMULA, the comparator drug, 1–2 sprays up to 6 times per day with not less than a 2-hour intervals between the doses. Both drugs should be taken when needed (a sore throat).

In view of the nature of drug intake (when needed), the lower margin of compliance will not be evaluated; the number of used doses is compared to maximum amounts stated in the protocol for the study drug (up to 5 sprays at once, not more than 10 times per day for Angal) or Prescribing Information for the comparator drug (up to 2 sprays at once, not more than 6 times per day for ANTI-ANGIN® FORMULA).

List of efficacy parameters

7 Efficacy evaluation

Primary outcome measure

7.1

The primary outcome measure was the percentage of patients without sore throat after 3 days of therapy, as evaluated by the Investigator according to the Tonsillopharyngitis Severity Score (TSS), in both Angal S and ANTI-ANGIN® FORMULA arms.

Secondary outcome measures

The secondary outcome measures in both therapy groups were:

- Frequency of ≥50% total score reduction according to the TSS questionnaire completed by the Investigator as compared to the baseline in both Angal S and ANTI-ANGIN® FORMULA groups at Visit 2 (Day 4).
- Total score reduction according to the TSS questionnaire, as well as a reduction in the symptoms (sore throat, difficulty in swallowing, salivation, erythema, and fever) after a 3-day therapy, at Visit 2 (Day 4), as compared to the baseline total score.
- A period of time required for disease symptoms relief, determined according to the patient's diary (subjective patient's evaluation), but no more than 5 days during the trial—for patients who have achieved the corresponding outcome.
- A proportion (%) of patients who fully recovered by Day 4 in Group A and by Day 5 in Group B (the outcome of a disease according to the objective evaluation by the Investigator, the total score according to the TSS questionnaire ≤2).
- A change in the sore throat intensity by 100 mm VAS (visual analogue scale filled in by the patient) at the beginning, after 3 days of therapy, and at the end of treatment in both groups.

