3. COURSE OF THE DISEASE

	ı v	Based on your subjective evaluation of the disease symptoms, can you say that you have improved so much that you do not need to use the spray anymore?
MORNING	HH:MM	YES / NO
DAY	HH:MM	YES / NO
EVENING	HH:MM	YES / NO

TE_003_ANG_LSP	THE PATIENT'S DIARY	PATIENT No

DAY 3: DD/MM/YYYY

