This trial has been designed and conducted to evaluate non-inferiority of the therapeutic efficacy and safety of the study drug Angal S, topical spray [menthol] containing 0.5 mg of lidocaine hydrochloride and 2 mg of chlorhexidine digluconate per ml (Sandoz d.d., Slovenia), when compared to ANTI-ANGIN® FORMULA, topical metered spray giving 0.12 mg of tetracaine hydrochloride and 0.24 mg of chlorhexidine bigluconate per dose (OOO Valeant, Russia) in the treatment of patients with uncomplicated acute infectious and inflammatory diseases of the pharynx accompanied by a sore throat. The objective of this Phase III trial is to demonstrate the non-inferior therapeutic efficacy of the study drug as compared to the reference product.

This Statistical Analysis Plan was developed in accordance with the following documents:

- Guidelines for examination of medicinal products, Vol. 1. Federal State Budgetary Institution Scientific Center for Expert Evaluation of Medicinal Products under the Ministry of Health of the Russian Federation (eds. A.N. Mironov). Moscow: Grif and K, 2013.
- ICH harmonized tripartite guideline. Statistical principles for clinical trials (E9). Current Step 4 version dated 5 February 1998.
- GCP rules of the Eurasian Economic Union (a draft).

The objective of this Statistical Analysis Plan is more detailed, compared to Section 9 of the trial protocol, description of the main principles of the protocol-based statistical analysis, description of the primary and secondary endpoints analysis methods, as well as other data obtained during the trial.

This Plan stipulates for consistence of the scheduled and conducted statistical analysis to the trial protocol, including definition of the analysis data sets, transformations and calculations for the endpoints, observations quantity needed, etc. No changes in this Statistical Analysis Plan compared to the trial protocol are envisaged.

2. Trial endpoints

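### The SAP excludes patients from the per-protocol set for more than three missed doses, although the protocol has both sprays used as needed and does not evaluate low use; early responders can be removed, and unequally by arm

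*SAP*

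**What the plan says.** SAP 3.2 gives a table of serious protocol deviations. One row reads "Low compliance: the patient missed more than 3 doses of the study drug", and its exclusion column says PP. The section adds that a sponsor representative evaluates every deviation, and that the decisions are documented before the analysis starts.

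Protocol 6.3 says that both drugs are used as needed for a sore throat. It continues: "In view of the nature of drug intake (when needed), the lower margin of compliance will not be evaluated". Use is compared only with the stated maximum in each arm. SAP 1 says: "No changes in this Statistical Analysis Plan compared to the trial protocol are envisaged".

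The schedules in SAP 3.1 differ in kind. Angal S is 6 to 10 times per day for 4 days or until full recovery, so it has a daily minimum. The comparator is "up to 6 times a day, for 5 days or until full recovery", a maximum with no minimum.

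The word dose is used in two ways. Protocol 4.4.4 says "One dose of Angal S is 3 to 5 consecutive presses", and 6.1 agrees. Protocol 4.4.3 says each patient in the study drug group "will be given 1 bottle (vial) of Angal S (150 doses"), which counts single presses. SAP Table 24 has a compliance column but no formula.

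PP is the additional analysis of the primary endpoint and ITT is the main one (Protocol 9.1.2, SAP 3.3 and 4.1.2).

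**The concern.** The SAP adds an under-use exclusion that the protocol rules out, and does not declare it as a change. The row also cannot be applied uniformly, because neither document gives a number of doses that should have been taken.

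It matters because use is tied to the outcome. The primary endpoint is absence of sore throat on Day 4, and the spray is taken for sore throat. The diary (Protocol Appendix 3) asks each day whether "you have improved so much that you do not need to use the spray". A patient whose pain resolves on Day 2 and who stops spraying is a treatment success, yet can look like a low complier. Excluding such patients conditions the PP set on the outcome. If this happens more in one arm, the PP difference shifts, and PP is the planned check on ITT in a non-inferiority trial.

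**Working it through.** **Step 1. What counts as missed.** More than 3 means 4 or more.

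| Reference count | Angal S | Comparator |
|---|---|---|
| Minimum, full course | 6 × 4 = 24 uses; excluded at 20 or fewer (83%) | none stated; nobody can miss a dose |
| Maximum, full course | 10 × 4 = 40; excluded at 36 or fewer (90%) | 6 × 5 = 30; excluded at 26 or fewer (87%) |
| First 3 days | 18 (minimum) to 30 (maximum) | 18 (maximum) |

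Over the three days before the Day 4 score, 18 uses is the floor in one arm and the ceiling in the other. An Angal S patient who is pain-free and stops after Day 2 is at least 6 uses below the minimum by the end of Day 3, and is still a Day 4 responder.

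**Step 2. What counts as a dose.** The bottle holds 30 ml and a press releases 0.15 to 0.20 ml (Protocol 2.1.1). 30 / 0.20 = 150, so the 150-dose figure reproduces only if a dose is one press. At 3 to 5 presses per dose the bottle holds 30 to 50 doses. Four missed Angal S doses are therefore 4 × 3 = 12 to 4 × 5 = 20 presses by the main definition, or 4 presses by the bottle count. The comparator has the same split: 1 to 2 sprays per dose in 4.4.4, 100 doses per bottle in 4.4.3.

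**Step 3. Effect on PP.** The plan gives no figure for this, so the removal shares are assumptions. Inputs: 140 randomized per arm, 65% (Angal S) vs 63% (Protocol 9.2), margin 14.5 points, two-sided 90% Newcombe interval. Non-inferiority is taken as a lower limit above −14.5 points, in line with the hypotheses in SAP 3.9. Removing a share f of the responders in an arm with true rate p leaves

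- p′ = p(1 − f) / (1 − pf)
- n′ = 140(1 − pf), rounded.

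Probabilities are exact binomial sums. For example, with f = 0.2 in the Angal S arm, p′ = 0.65 × 0.8 / 0.87 = 0.598, n′ = 122, and the difference is 0.598 − 0.630 = −0.032.

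Angal S responders only, as counting against the minimum would allow, truth 65% vs 63%:

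| Share removed | Angal S n′ | p′ | PP difference (points) | Chance of PP non-inferiority |
|---|---|---|---|---|
| 0 | 140 | 0.650 | +2.0 | 90% |
| 10% | 131 | 0.626 | −0.4 | 78% |
| 20% | 122 | 0.598 | −3.2 | 60% |
| 30% | 113 | 0.565 | −6.5 | 37% |

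From 128 per arm, the number planned to complete per protocol, the starting chance is 87% rather than 90%.

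Opposite direction, truth on the margin (48.5% vs 63%):

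| Responders removed, Angal S / comparator | False PP non-inferiority |
|---|---|
| none | 4.9% |
| equal, 10/20/30% in both | 4.8 / 5.2 / 4.9% |
| 10% / 20% | 11.6% |
| 20% / 30% | 12.8% |
| comparator only, 10/20/30% | 11 / 23 / 40% |

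Equal removal does no harm to the error rate. The damage comes from imbalance.

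**The case against.** Several points stand against a stronger reading.

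- **Role of PP.** It is the additional analysis. A reader might infer that the row threatens the main result. It does not: ITT membership does not depend on it.
- **False non-inferiority.** A reader might take the 40% figure as the expected error. It requires responders to be lost from the comparator arm alone, and no counting rule in the documents clearly produces that. Counting against the maximum, or against 18 uses in three days, also catches Angal S patients who stop early. Comparator-only removal is an upper extreme.
- **Meaning of dose.** The documents mostly define a dose as one administration, and the diary logs numbered administrations without a field for presses. The 4-press reading is possible but strained. The inconsistency is secondary to the missing reference count.
- **Existing safeguards.** Treatment ends at full recovery, and exclusions are decided case by case before analysis. These help, but only partly. SAP 3.2 does not exempt doses after recovery. Recovery is a total TSS of 2 or less scored by the investigator, and the protocol synopsis says: "During Days 2 and 3 of the therapy, the patients (in both groups) do not visit the trial site". The case-by-case review has no counting criterion, and the trial is open-label.
- **Protocol 6.3 is not the only protocol text.** Protocol 4.4.4 and 6.1 give Angal S a daily range with a minimum, while 6.3 says as needed. The protocol is inconsistent with itself, so the SAP row is not the only text that needs attention.
- **Defining instead of deleting.** One could keep the row and not count doses after recorded recovery. That would keep PP more distinct from ITT, but it still needs a reference count, and the comparator schedule supplies no minimum.

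**Conclusion.** The contradiction between SAP 3.2 and Protocol 6.3 is certain from the text, as is the absence of any count against which a dose is missed. It follows that the row can remove early responders from PP, and unequally by arm.

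The clearest case is counting against the stated minimum, where only Angal S patients can be excluded. The PP difference then moves against Angal S, and the chance of PP non-inferiority drops from 90% to between 78% and 37% for assumed removal of 10% to 30% of its responders. Bias in favour of Angal S needs more comparator than Angal S responders removed. A 10-point imbalance in the removal shares gives about 12 to 13% false non-inferiority against 4.9%.

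These figures rest on assumed shares, on removing responders only, and on 140 per arm before other PP exclusions. The documents support neither a particular size nor a particular direction. The point should be corrected before the deviation list is fixed, but it concerns a supportive analysis only.

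**What to change.** 1. Delete the missed-doses row from SAP 3.2, so that it agrees with Protocol 6.3.
2. Deletion alone is not enough, because PP also requires completion of the prescribed treatment period. State in SAP 3.3 and Protocol 9.7 that low use, or stopping the spray because symptoms have resolved, is neither a significant deviation nor a failure to complete treatment for PP purposes.
3. Clarify that the non-compliance item in Protocol 5.3.1 (item 8) does not bring under-use back as a PP exclusion.
4. The sponsor must reconcile the Angal S schedule in Protocol 4.4.4 and 6.1 and SAP 3.1 with the as-needed statement in Protocol 6.3. No dosing rule is proposed here.
5. In SAP Table 24, report uses per day and use above the stated maximum by arm, in one stated counting unit.

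Cost: a few lines of SAP text. The diary and returned-spray data are already collected. PP keeps low users and moves closer to ITT, so it is a less distinct check. The Protocol 9.7 wording may need a formal amendment, since Protocol 11.2 classes changes that may influence the statistical methods as significant.
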